- 11. Have a history of significant active or unstable major depressive disorder or other severe psychiatric disorder (for example, schizophrenia, bipolar disorder, or other serious mood or anxiety disorder) within the last 2 years

Note: Participants with major depressive disorder or generalized anxiety disorder whose disease state is considered stable for the past 2 years and expected to remain stable throughout the course of the study, in the opinion of the investigator, may be considered for inclusion if they are not on excluded medications

- 12. Have any lifetime history of a suicide attempt
- 13. Have a Patient Health Questionnaire-9 (PHQ-9) score of 15 or more at Visit 1 or 3, prior to randomization
- 14. On the Columbia-Suicide Severity Rating Scale (C-SSRS) at Visits 1 or 3, prior to randomization:
 - a. a "yes" answer to either Question 4 (Active Suicidal Ideation with Some Intent to Act, Without Specific Plan)

or

b. a "yes" answer to Question 5 (Active Suicidal Ideation with Specific Plan and Intent) on the "Suicidal Ideation" portion of the C-SSRS

c. a "yes" answer to any of the suicide-related behaviors (Actual Attempt, Interrupted Attempt, Aborted Attempt, Preparatory Act or Behavior) on the "Suicidal Behavior" portion of the C-SSRS

and

- d. the ideation or behavior occurred within the past month
- 15. Have any of the following cardiovascular conditions within 3 months prior to randomization:
 - · acute myocardial infarction
 - cerebrovascular accident (stroke)
 - · unstable angina
 - · hospitalization due to congestive heart failure
 - · uncontrolled hypertension (systolic blood pressure above or equal to 160 mmHg and/or diastolic blood pressure above or equal to 100 mmHg)
- 16. Have New York Heart Association Functional Classification IV congestive heart failure
- 17. Have a serum calcitonin level (at Visit 1) of 35 ng/L or more, as determined by central laboratory at Visit 1

- 18. Have a family or personal history of medullary thyroid carcinoma or Multiple Endocrine Neoplasia Syndrome type 2
- 19. Have a history of an active or untreated malignancy or are in remission from a clinically significant malignancy (other than basal- or squamous-cell skin cancer, in situ carcinomas of the cervix, or in situ prostate cancer) for less than 5 years
- 20. Have any other condition not listed in this section (for example, hypersensitivity or intolerance) that is a contraindication to GLP-1R agonists

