8.1.3. Exploratory Efficacy Assessments

The following exploratory assessment will be collected at the times shown in the Schedule of Activities (Section 1.3).

Obesity-related health problems

- Proportion of participants who achieved the following improvements of obesity-related health problems at 72 weeks regardless of BMI at baseline;
 - o Achieved improvement in ≥2 obesity-related health problems for participants with baseline BMI ≥27 and <35 kg/m²
 - o Achieved improvement in ≥1 obesity-related health problems for participants with baseline BMI ≥35 kg/m²
 - Achieved 2 or 3 improvements (only for participants with 3 defined obesity-related health problems) regardless of BMI at baseline
 - Achieved 2 improvements (only for participants with 2 defined obesity-related health problems regardless of BMI at baseline)
 - Achieved 1 improvement (only for participants with 1 defined obesity-related health problem regardless of BMI at baseline)

Other parameters

- Adiponectin (μg/mL) (both high molecular weight and total adiponectin, measured at central laboratory)
- Leptin (pg/mL) (measured at central laboratory)
- high-sensitivity C-reactive protein (hsCRP) (ng/dL) (measured at central laboratory)
- TNF-α (pg/mL) (measured at central laboratory)
- eGFR (mL/min/1.73 cm²) (creatinine measured at central laboratory) calculated using the Japanese Society of Nephrology formula: 194 × Cr 1.094 × Age 0.287 [if female; × 0.739]
- Urinary albumin/creatinine ratio (mg/gCre) (measured at central laboratory)

Incident Diabetes

- Time to onset of T2DM during the 72-week treatment period
 - o Definition and Management of Incident Diabetes

Definition of incident diabetes

Incident diabetes is followed by Japanese Clinical Practice Guideline for Diabetes 2019 (Araki et al. 2020) and defined when any 1 of the following occur after randomization:

- unequivocal hyperglycemia (random glucose ≥200 mg/dL) with signs or symptoms of hyperglycemia (e.g., dry mouth, polyposia, polyuria, body weight loss, or diabetic retinopathy).
- within a 4-week period, the following laboratory evidence of diabetic type criteria including either HbA1c ≥6.5%, or glucose levels (fasting glucose or OGTT 0-hour glucose ≥126 mg/dL and/or OGTT 2-hour glucose ≥200 mg/dL) are observed:
 - i. Both glucose level and HbA1c meets diabetic type criteria

- ii. Only glucose level meets diabetic type criteria
 - With typical symptoms of DM or definite diabetic retinopathy

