#### 4.4.1.2. Defined Obesity-Related Health Problems

The definition of baseline obesity-related health problems (ORHPs) are:

- IGT from 2-hour OGTT results: Fasting glucose or 0-hour OGTT = 110-125 mg/dL (6.1-6.9 mmol/L) and/or 2-hour OGTT = 140-199 mg/dL (7.8-11.0 mmol/L).
- **Hyperlipidemia**: triglyceride (TG) ≥150 mg/dL at baseline
- NAFLD: HFF  $\geq$ 5% by MRI at baseline

Definition of IGT is based on the GPHZ protocol (b). For each subjects, baseline ORHPs are determined by the measurements (not by the inputs of IWRS).

The definition of improvements of each defined obesity-related health problems are:

- **IGT** (only for participants with IGT at baseline)
  - o Return to normal blood glucose range
    - OGTT 0-hour glucose <110 mg/dL AND

- OGTT 2-hour glucose <140 mg/dL
- **Hyperlipidemia** (only for participants with hyper-triglyceridemia [triglyceride (TG) ≥150 mg/dL] at baseline)
  - o Return to normal range (TG <150 mg/dL) OR
  - o Reduced by 30% from baseline
- NAFLD (only for participants with diagnosis of NAFLD [HFF ≥5%] by MRI at baseline)
  - o Return to normal range (HFF <5%) OR
  - o Reduced by 30% from baseline

Incident diabetes is followed by Japanese Clinical Practice Guideline for Diabetes 2019 (Araki et al. 2020) and defined when any 1 of the following occur after randomization:

- unequivocal hyperglycemia (random glucose ≥200 mg/dL) with signs or symptoms of hyperglycemia (e.g., dry mouth, polyposia, polyuria, body weight loss, or diabetic retinopathy).
- within a 4 week period, the following laboratory evidence of diabetic type criteria including either HbA1c ≥6.5%, or glucose levels (fasting glucose or OGTT 0 hour glucose ≥126 mg/dL and/or OGTT 2 hour glucose ≥200 mg/dL) are observed:
  - o Both glucose level and HbA1c meets diabetic type criteria
  - o Only glucose level meets diabetic type criteria
    - With typical symptoms of DM or definite diabetic retinopathy
    - Without typical symptoms of DM or definite diabetic retinopathy, re-exam within 1 month and:
      - Both glucose level and HbA1c meets diabetic type criteria
      - Only glucose level meets diabetic type criteria
      - Only HbA1c meets diabetic type criteria
  - o Only HbA1c meets diabetic type criteria, re exam within 1 month and
    - Both glucose level and HbA1c meet diabetic type criteria
    - Only glucose level meets diabetic type criteria
- initiation of any medication for the treatment of diabetes

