#### 4.4.1.5. Definition of parameters related to 2-hour OGTT

The following parameters will be collected during 2-hour OGTT for each scheduled OGTT visit:

- glucose
- insulin, and
- C-peptide.

For each above parameter, the mean concentration over 120 minutes plots will be created by glycemia status at randomization and by treatment group and by OGTT visit (that is, at baseline and at Week 72).

For each above parameter, the area under the curve from time zero to 2 hours  $(AUC)_{(0-2h)}$  during OGTT will be calculated using the trapezoidal rule. The respective  $AUC_{(0-2h)}$  will be summarized by treatment group and by OGTT visit.

In addition, the following OGTT derived parameters (Araki et al. 2020) will be calculated at each OGTT visit for each participant with OGTT:

- Glycemic response categories:
  - o Normal:
    - OGTT 0 hour glucose <110 mg/dL AND
    - OGTT 2-hour glucose <140 mg/dL

  - Borderline type:
    - OGTT 0 hour glucose =110-125 mg/dL (6.1-6.9 mmol/L) **OR**
    - OGTT 2-hour glucose =140-199 mg/dL (7.8-11.0 mmol/L)
  - o Suspected T2DM:
    - o OGTT 0 hour glucose ≥126 mg/dL AND
    - o OGTT 2-hour glucose ≥200 mg/dL
- Matsuda Index =  $\frac{10000}{\sqrt{(FPG \times FPI) \times (\bar{G} \times \bar{I})}}$ , where FPG is the fasting glucose, FPI is the fasting insulin,  $\bar{G}$  denotes the mean glucose during OGTT, and  $\bar{I}$  denotes the mean insulin during OGTT

- Insulin secretion =  $\left(\frac{\Delta C_{\text{pep}}}{\Delta G}\right)_{0-120}$ , where  $\Delta C_{\text{pep}}$  denotes the incremental area under the plasma C-peptide curve during the 2-hour OGTT, and  $\Delta G$  denotes the incremental area under the plasma glucose concentration curve during 2-hour OGTT
  - O Insulin secretion index =  $\frac{\left(\frac{\Delta C_{pep}}{\Delta G}\right)_{0-120}}{normal\ level\ of\ insulin\ secretion}$ , where normal level of insulin secretion is the median value for insulin secretion, ie,  $\left(\frac{\Delta C_{pep}}{\Delta G}\right)_{0-120}$ , in participants with normal glucose tolerance at baseline
  - o Normal insulin secretion: insulin secretion index >70%
  - Moderate impairment of insulin secretion: 50% to 70% (inclusive) of the insulin secretion index
  - o Severe impairment of insulin secretion: <50% of the insulin secretion index

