Change in eGFR	Mean change from BL in • eGFR	Efficacy analysis set	MMRM model in Section 4.3.2.1	Exploratory objective added to protocol planned analyses

Analysis variable	Criteria/Measures	Analysis set	Analysis method	Additional Information
Shift in eGFR	Shift table of minimum baseline to minimum postbaseline	Efficacy analysis set		Exploratory objective added to protocol planned analyses
Change in UACR	Mean change from BL in UACR	Efficacy analysis set	MMRM model in Section 4.3.2.1	Exploratory objective added to protocol planned analyses
Improvement of hyperuricemia (72 weeks)	Proportion of participants who achieved improvements of hyperuricemia. Definition of improvement of hyperuricemia: Uric acid 7 mg/dL	Efficacy analysis set – participants with hyperuricemia at BL defined as uric acid > 7 mg/dL	Longitudinal logistic model in Section 4.4.2.3	Exploratory objective added to protocol planned analyses
Improvement of hypertension (72 weeks)	Proportion of participants who achieved improvements of hypertension. Definition of improvement of hypertension: Diastolic blood pressure <80 mmHg or Systolic blood pressure <130 mmHg.	Efficacy analysis set – participants with hypertension at BL defined as diastolic blood pressure ≥80 mmHg or Systolic blood pressure ≥130 mmHg.	Logistic model in Section 4.4.2.2	Exploratory objective added to protocol planned analyses
Change in NAFLD related parameters (24, 52, and 72 weeks)	Mean change from BL in  NAFLD fibrosis score	(1) Efficacy analysis set; (2) Efficacy analysis set - participants with NAFLD at BL	MMRM model in Section 4.3.2.1	Exploratory objective added to protocol planned analyses

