# 4.9. Changes to Protocol-Planned Analyses

Efficacy analysis set for imaging data has been modified to accommodate the allowance of measurement schedule.

Added following exploratory objectives:

- Improvement of hyperuricemia (defined by uric acid ≤7.0 mg/dL).
- Improvement of hypertension: Diastolic blood pressure <80 mmHg or Systolic blood pressure <130 mmHg.
- Achievement of ALT ≤30 U/L.
- Changes in NAFLD fibrosis score.

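### Two SAP definitions use the wrong AND/OR operator: one raised blood pressure component already counts as hypertension improved at baseline, and one diabetic-range OGTT value is shut out of Suspected T2DM

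*SAP*

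**What the plan says.** **Hypertension.** Improvement of hypertension at 72 weeks is an exploratory objective added in the SAP. Table GPHZ.4.4 gives the analysis population as "participants with hypertension at BL defined as diastolic blood pressure ≥80 mmHg or Systolic blood pressure ≥130 mmHg" and the response as "Definition of improvement of hypertension: Diastolic blood pressure <80 mmHg or Systolic blood pressure <130 mmHg". Section 4.9 repeats the response rule: "Improvement of hypertension: Diastolic blood pressure <80 mmHg or Systolic blood pressure <130 mmHg". The arms are compared with the logistic model of SAP 4.4.2.2.

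**OGTT categories.** SAP 4.4.1.5 derives three glycemic response categories at each OGTT visit:

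- Normal: 0-hour <110 and 2-hour <140 mg/dL.
- Borderline: 0-hour 110–125 or 2-hour 140–199 mg/dL.
- Suspected T2DM: "OGTT 0 hour glucose ≥126 mg/dL AND" 2-hour ≥200 mg/dL.

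The incident diabetes definition in SAP 4.4.1.2 describes a diabetic-type glucose result at the same cut-offs as "OGTT 0 hour glucose ≥126 mg/dL and/or OGTT 2 hour glucose ≥200 mg/dL". Protocol 8.1.3 agrees: "OGTT 0-hour glucose ≥126 mg/dL and/or OGTT 2-hour glucose ≥200 mg/dL".

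**The concern.** For hypertension, entry and response are both joined by *or*, so the two sets overlap and a participant can be a responder with no change in blood pressure. Someone who worsens from 150/75 to 170/78 is still counted as improved at Week 72, because DBP remains below 80. Someone with both components raised becomes a responder when only one of them falls below its limit. A reported percentage improved would then not mean what a reader takes it to mean.

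For the OGTT categories, a participant with one diabetic-range value is called Borderline or gets no label, although the same SAP treats that reading as diabetic type elsewhere. The derived variable would contain blanks and would disagree with the incident diabetes criteria.

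**Working it through.** The plan states no figure for either definition, so there is none to reproduce. The check is of logic first and of assumed size second.

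**1. Hypertension, logic.** Entry is H = (DBP ≥80 or SBP ≥130). By De Morgan's rule, not-H = (DBP <80 and SBP <130). The SAP response is (DBP <80 or SBP <130), which is a larger set. Enumerating integer SBP 90–199 and DBP 50–119:

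| Baseline pattern | Value pairs | Improved at baseline, *or* rule | Improved at baseline, *and* rule |
|---|---|---|---|
| SBP only raised | 70 × 30 = 2100 | 2100 (100%) | 0 |
| DBP only raised | 40 × 40 = 1600 | 1600 (100%) | 0 |
| Both raised | 70 × 40 = 2800 | 0 | 0 |

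These are value pairs, not participants. The 100% and 0% results need no assumption.

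The SAP's handling of IGT shows the consistent form. Entry is and/or; improvement in 4.4.1.2 is "OGTT 0-hour glucose <110 mg/dL AND" 2-hour <140 mg/dL. Hyperuricemia is also a clean complement: entry above 7 mg/dL, improvement at ≤7.0 mg/dL in Section 4.9. For triglycerides and HFF, nobody meets the improvement rule on their own baseline value.

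**2. Hypertension, size (assumed).** Take SBP and DBP as bivariate normal, truncated at the entry limit in Protocol 5.2, which excludes "uncontrolled hypertension (systolic blood pressure above or equal to 160 mmHg and/or diastolic blood pressure above or equal to 100 mmHg". Then

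share already improved = P(exactly one component raised) / P(at least one raised).

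Example: means 130/82.5, SD 14/10, correlation 0.6. SBP only 0.107, DBP only 0.209, both 0.369. Share = (0.107 + 0.209) / (0.107 + 0.209 + 0.369) = 0.316 / 0.685 = 46%.

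- Means 125–135/80–85, SD 12–16/8–12, correlation 0.5–0.8: 24.9% to 64.3%.
- Same SDs, means 120–140/75–90, correlation 0.4–0.8: 17.7% to 88.1%, median 54%.

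**3. Hypertension at Week 72 (assumed).** Twenty-four simulated scenarios: means 125–135/80–85, SD 14/10, SBP–DBP correlation 0.5 or 0.7, baseline-to-Week-72 correlation 0.6, placebo change −1/0, active change −6/−3 or −10/−5 mmHg.

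| Arm | Improved, *or* rule | Improved, *and* rule |
|---|---|---|
| Placebo | 41–67% | 14–28% |
| Active | 57–87% | 25–53% |

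The risk difference was larger under *or* in 15 of 24 scenarios and the odds ratio in 12 of 24. The absolute rates rise in every arm; the contrast moves in no consistent direction.

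**4. OGTT categories.** One example per combination, in mg/dL (0-hour/2-hour):

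| Reading | Category under SAP 4.4.1.5 | Diabetic-type glucose under SAP 4.4.1.2 |
|---|---|---|
| 100/120 | Normal | no |
| 100/160 | Borderline | no |
| 100/210 | none | yes |
| 115/120 | Borderline | no |
| 115/160 | Borderline | no |
| 115/210 | Borderline | yes |
| 130/120 | none | yes |
| 130/160 | Borderline | yes |
| 130/210 | Suspected T2DM | yes |

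Five of nine combinations contain a diabetic-range value: 1 Suspected T2DM, 2 Borderline, 2 unlabelled. With Suspected T2DM as and/or, and Borderline as the remainder, all nine fall in exactly one category. These are combinations, not shares of participants.

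**The case against.** - **Little depends on the OGTT category.** No planned comparison in the SAP uses it. Table GPHZ.4.4 takes the Matsuda index, insulin secretion and beta-cell function from the same section, but not the category, and incident T2DM has its own definition. This stands, and it keeps the second half secondary.
- **The strict OGTT rule might be intended.** The label says suspected, and a single raised glucose value does not by itself establish incident diabetes in SAP 4.4.1.2. But a deliberately strict label would not explain leaving 100/210 and 130/120 without any category, or calling 115/210 Borderline.
- **The *and* rule is not the only repair for hypertension.** Requiring each component raised at baseline to normalise would also stop anyone qualifying on the baseline reading. That is true, but the SAP text does not say it, and the *and* rule matches the SAP's own treatment of IGT.
- **The comparison remains valid under the null.** Randomization spreads the already-improved participants evenly across arms in expectation, and mean changes in SBP and DBP are reported separately. This stands. The damage is to the meaning of the responder percentages.
- **The 25–64% depends on the assumptions.** It does, and the wider 18–88% shows how strongly. Only the logical result is certain.

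**Conclusion.** Both definitions are wrong as written. With certainty, 100% of participants with exactly one raised blood pressure component meet the hypertension response rule at baseline, against 0% under an *and* rule. Likewise every OGTT reading with only one diabetic-range value is kept out of Suspected T2DM. The hypertension responder rate can only be equal or higher in each arm, because everyone who satisfies the *and* rule also satisfies the *or* rule. The share of the hypertensive group affected at baseline cannot be computed from the documents; 25–64% rests on the blood pressure distribution assumed above.

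Severity is minor. One exploratory endpoint and one derived variable are affected. The co-primary endpoints, IGT improvement, time to onset of T2DM and mean change in blood pressure use other definitions and are unaffected.

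**What to change.** 1. In SAP Table GPHZ.4.4 and in Section 4.9, define improvement of hypertension as DBP <80 mmHg **and** SBP <130 mmHg, the exact complement of the baseline definition.
2. In SAP 4.4.1.5, define Suspected T2DM as 0-hour ≥126 and/or 2-hour ≥200 mg/dL, matching 4.4.1.2, and Borderline as neither normal nor diabetic type. The three categories are then exclusive and exhaustive.

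The cost is SAP wording in three places and the matching derivation code, best settled before unblinding. No new data are needed. When editing, note that the baseline IGT wording in 4.4.1.2 also sets no upper limit on the other glucose value, so 115/210 would read as IGT there. The diabetes exclusion at entry limits the effect, and neither change depends on it.

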# 4.5. Safety Analyses

Unless specified otherwise, safety assessments will be based on the SS (Table GPHZ.3.1). All data collected between randomization and the end date of study participation will be included, regardless of the adherence to study drug.

The statistical assessment of homogeneity of the distribution of categorical safety responses, between tirzepatide doses and placebo, will be conducted using Fisher's exact test, unless specified otherwise.

The mean change from baseline differences among treatments at all scheduled visits will be assessed via an MMRM using REML. Unless specified otherwise, if the safety parameter is assessed at the 72 weeks, then the model will include treatment group, visit and treatment-by-visit interaction and stratification factors as fixed effects, and baseline value of the safety parameter as a covariate. To model the covariance structure within participants, the unstructured covariance matrix will be used. If this model fails to converge, the covariance structures specified in Section 4.3.2.1 will be tested in order until met convergence. If the data does not warrant the MMRM model, then ANCOVA model will be conducted.

For selected safety parameters, time-to-first-event analysis via the Cox-proportional hazards model may be conducted. Participants without the event will be censored at the end of study participation. For participants experiencing the event, the "time-to-first-event" will be the time (in weeks) from first dose to first occurrence of the event.

Where necessary, the rate of events will be analyzed using a generalized linear mixed-effects model, assuming the number of events follow a negative binomial distribution and with treatment as a fixed effect. The logarithm of days during the active treatment period will be adjusted as an offset, to account for possible unequal treatment duration of follow-up among participants.

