# 3. Analysis Sets

For purposes of analysis, the following populations are defined:

Table GPHZ.3.1. Description of Analysis Populations

Population	Description
Entered	All participants who sign informed consent form (ICF)
Randomized	All participants who are randomly assigned a study drug.
Modified Intent-to-Treat (mITT)	All randomly assigned participants who are exposed to at least 1 dose of study drug. Participants will be included in the treatment group to which they were randomized.

Table GPHZ.3.2. Description of Analysis Datasets

Analysis Datasets	Description
Efficacy Analysis Set (EAS)	Data obtained during the treatment period from the modified intent-to-treat (mITT) population, excluding data after discontinuation of study drug (last dose date + 7 days)
	Regarding imaging measurements (MRI and CT), data obtained during the treatment period from the mITT population, excluding data after discontinuation of study drug (last dose date + 14 days)
Full Analysis Set (FAS)	Data obtained during treatment period from the mITT population, regardless of adherence to study drug.
Safety Analysis Set (SS)	Data obtained during the treatment plus follow up period from the mITT population, regardless of adherence to study drug.

Unless otherwise specified, for analyses guided by the "efficacy" estimand, EAS will be used. For analyses guided by the "treatment-regimen" estimand, FAS will be used. For safety analysis, SS will be used.

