Analysis Dataset	Analysis Type	Baseline	Postbaseline
SS	1.1) Treatment-Emergent Adverse Events	The baseline period is defined as the start of screening and ends prior to the first dose in of study treatment (typically at Week 0).	Starts after the first dose of study treatment and ends at the end of the study period (including off-drug follow up visit).
SS	1.2) Treatment-Emergent Abnormal Labs a , Vital Signs, and ECGs.	Baseline will include all scheduled and unscheduled measurements during the baseline period (Visit 1 to Visit 3)	Postbaseline will be defined as above (1.1). All scheduled and unscheduled measurements will be included.
SS	1.3) Change from Last Baseline to Week xx and to Last Postbaseline for Labs a ,Vital Signs, and ECGs.	The last scheduled and unscheduled non-missing assessment recorded during the baseline period defined above (1.2).	Postbaseline will be defined as above (1.1). Only scheduled visits will be included. The early discontinuation (ED) visits are considered scheduled visits.

Table GPHZ.4.1. Baseline and Postbaseline Definitions for Safety Analysis

Abbreviations: ECGs = electrocardiogram; SS = Safety Analysis Set.

For the primary and secondary efficacy endpoint analyses, data for participants with missing values at the 72-week visit will be imputed based on the method described in Section 4.3.2. Otherwise, missing values will not be explicitly imputed except for the parameters with only 1 postbaseline measure during the analysis period per schedule of activity, where last observation carried forward (LOCF) approach will be applied to impute the endpoint when ED measure is available.

End of study participation for a participant will be the earliest of date of death, date of withdrawal from further participation in the study, or date of safety follow-up visit (Visit 801). For participants considered to be lost-to-follow-up, end of study participation will be the date of lost-to-follow-up reported by the investigator. Participant data included in the database after the last date of study participation (including safety follow-up period) will be excluded from statistical analysis.

Statistical treatment comparisons will only be performed between tirzepatide 10 mg or 15 mg, and placebo. Since the trial is not adequately powered to detect difference among tirzepatide doses, comparisons among tirzepatide doses will not be performed unless otherwise specified.

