#### 4.5.1. Extent of Exposure

Summary of duration of follow-up (defined as time in days from date of randomization to the date of the last study visit) and/or duration on study treatment (defined as time in days from date of first dose of study treatment to date of last dose of study treatment plus 7 days) will be provided by treatment group using data from SS.

For the summary of duration on study and study treatment, the frequency and percentage of participants falling into the following range will be summarized by planned treatment group as well:

- >()
- ≥4 weeks
- >8 weeks
- ≥12 weeks
- >16 weeks
- >20 weeks

- >24 weeks
- >36 weeks
- >48 weeks
- ≥52 weeks
- >72 weeks

In addition, the frequency and percentages of participants falling into the following exposure ranges for study and study treatment may be summarized by planned treatment group:

- 0 weeks
- >0 to <4 weeks
- >4 to <8 weeks
- >8 to <16 weeks
- $\geq$ 16 to  $\leq$ 24 weeks
- >24 to <36 weeks
- >36 to <48 weeks
- >48 to <52 weeks
- >52 to <72 weeks
- >72 weeks

No p-values will be reported in these summaries as they are intended to describe the study populations, rather than test hypotheses about them.

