# Other hypoglycemia categories:

• **Nocturnal hypoglycemia** is defined as any hypoglycemic event that occurs between bedtime and waking.

To avoid duplicate reporting, all consecutive hypoglycemic events occurring within a 1-hour period will be considered as a single hypoglycemic event.

Statistical summaries and analyses will exclude hypoglycemic events occurring after initiation of rescue antihyperglycemic medication. Both the incidence (percent of participants experiencing ≥1 episode) and the rate (episodes/patient/year) of level 2 or level 3 hypoglycemia, and level 3 hypoglycemia will be reported by treatment.

The incidence of hypoglycemic events will be analyzed using logistic regression with treatment and stratification factors as fixed effects. The rate of hypoglycemic episodes per patient year may be analyzed using a generalized linear mixed-effects model assuming the number of hypoglycemic episodes follows a negative binomial distribution with the mean modeled using stratification factors and treatment as fixed effects. A listing of hypoglycemic events will be provided.

If a hypoglycemic event meets the criteria of severe, the event would specifically be collected as an SAE. Serious hypoglycemia is defined by pharmacovigilance criteria and will also be captured with a SAE form.

[figure not shown]
Severe/serious hypoglycemia will be considered as AESIs. The summaries of severe/serious hypoglycemia will be provided by treatment group, if deemed necessary.

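### Safety event rates count events over a longer window than the model offset covers, and hypoglycemic events are cut at rescue medication with no matching cut in time at risk

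*SAP*

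**What the plan says.** **Events counted.** SAP 4.5 sets the scope of the safety analyses: "All data collected between randomization and the end date of study participation will be included, regardless of the adherence to study drug". The Safety Analysis Set in SAP 3 (Table GPHZ.3.2) agrees: "Data obtained during the treatment plus follow up period from the mITT population, regardless of adherence to study drug". Table GPHZ.4.1 in SAP 4.1 runs the postbaseline period for adverse events through the off-drug follow-up visit.

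**Time in the denominator.** For event rates, to be modelled where necessary with a negative binomial distribution, SAP 4.5 says: "The logarithm of days during the active treatment period will be adjusted as an offset". The reason given is "to account for possible unequal treatment duration of follow-up among participants". The SAP does not define the *active treatment period*. On-drug time appears in SAP 4.5.1 under another name, duration on study treatment: "time in days from date of first dose of study treatment to date of last dose of study treatment plus 7 days". The Full Analysis Set, by contrast, uses the treatment period without regard to drug intake: "Data obtained during treatment period from the mITT population, regardless of adherence to study drug".

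**Hypoglycemia.** SAP 4.5.5.4 says: "Statistical summaries and analyses will exclude hypoglycemic events occurring after initiation of rescue antihyperglycemic medication". Episodes per patient per year, for level 2 or 3 and for level 3, are to be reported by treatment. A negative binomial model of that rate is optional. The section states no denominator, no offset and no end to time at risk at rescue.

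**The concern.** A rate is interpretable only if the events and the person-time come from the same interval. Here the two intervals differ within one section of the SAP. The time-to-first-event analysis in the same section does censor at the end of study participation, so two models for safety events use different clocks.

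Off-drug events will exist to be counted. Protocol 7.1 keeps participants who stop drug in the study for all planned safety measurements. Table 3 of the Schedule of Activities collects adverse events and hypoglycemic events at Visit 99, the early discontinuation visit and Visit 801.

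For hypoglycemia a second mismatch runs the other way: events disappear after rescue while the time can run on. Under Protocol 6.5, glucose-lowering medication is open to participants who develop diabetes. Protocol 4.1 enriches the population to more than 60% with impaired glucose tolerance, and delayed progression to diabetes on tirzepatide is an exploratory objective.

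At stake are the reported hypoglycemia rate and any other event rate analysed with this offset.

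**Working it through.** The documents state no event rate, exposure total or rate ratio, so there is no planned figure to reproduce. The check is the factor by which an arm's pooled rate is distorted, as an approximation to the negative binomial model.

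**Inputs from the documents.** Treatment period 72 weeks; safety follow-up 4 weeks, so participation to Week 76; on-drug time ends 7 days after the last dose.

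**Assumed inputs.** Share stopping drug *q*; week of last dose; off-drug event rate as a fraction *r* of the on-drug rate; share and week of rescue. The 25% dropout in SAP 5 is for power only. It is neither given by arm nor specific to stopping drug.

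**1. Planned-period reading.** For participants followed to the end at a constant event rate, the factor is 76/72 = 1.056 in every arm.

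**2. On-drug reading.** With *s* on-drug weeks for those who stop and follow-up to Week 76:

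factor = [(1 − q)(72 + 4r) + q(s + (76 − s)r)] / [(1 − q)72 + q·s]

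Take a last dose at Week 20, so s = 21.

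- q = 0.25: denominator 0.75 × 72 + 0.25 × 21 = 59.25.
  - r = 1: 76/59.25 = 1.28.
  - r = 0.5: (0.75 × 74 + 0.25 × 48.5)/59.25 = 67.625/59.25 = 1.14.
  - r = 0: 59.25/59.25 = 1.00.
- q = 0.10, r = 1: 76/(0.90 × 72 + 0.10 × 21) = 76/66.9 = 1.14.
- Last dose at Week 8 or Week 36 instead, q = 0.25, r = 1: 76/56.25 = 1.35 or 76/63.25 = 1.20.

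**3. Effect on the rate ratio, on-drug reading, r = 1.** If one arm has 25% stopping and the other 10%, the ratio of the first to the second is biased by 1.17 to 1.08 for last doses from Week 8 to Week 36. With the arms reversed it is 0.86 to 0.92. With the same stopping pattern in both arms it is 1.00.

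**4. If those who stop leave the study 4 weeks later** (s = 21, r = 1):

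- q = 0.25: (0.75 × 76 + 0.25 × 25)/59.25 = 63.25/59.25 = 1.07.
- q = 0.10: (0.90 × 76 + 0.10 × 25)/66.9 = 70.9/66.9 = 1.06.
- The ratio between such arms is biased by less than 1%.

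**5. Hypoglycemia.** Events are cut at rescue in week *w*, with a full 72-week denominator:

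factor = [(1 − q)72 + q·w]/72

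- 10% rescue: 67.2/72 = 0.933 at Week 24; 70/72 = 0.972 at Week 52.
- 1% rescue: 71.52/72 = 0.993 at Week 24; 71.8/72 = 0.997 at Week 52.
- With 10% rescue on placebo and 1% on tirzepatide, the tirzepatide/placebo ratio is biased by 0.993/0.933 = 1.06 (Week 24) or 0.997/0.972 = 1.03 (Week 52).
- With 20% versus 2%, the same formula gives 1.14 and 1.05.

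**6. After matching.** If events and person-time share one window, the factor is 1.00 in every arm by construction.

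**The case against.** A reader might infer that the rates are wrong by different amounts in each arm. The documents do not support that. The on-drug reading is only one candidate for an undefined term, and the planned 72 weeks fits the way the treatment period is used for the Full Analysis Set. A difference between arms also needs different stopping patterns and events that continue off drug. Protocol 2.2 reports dose-dependent gastrointestinal events and treatment discontinuations because of them, which makes unequal stopping plausible but puts no figure on it. Nor is it certain how long those who stop are followed: Protocol 7.1 keeps them in the study, while Protocol 7.2 and the early discontinuation visit also provide for leaving it.

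A reader might also take injection-site reactions as a clear case of inflation. They point the other way. Once injections stop, new reactions should be few, so on-drug time is close to the right denominator and total participation time would dilute the rate.

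For hypoglycemia, a participant rescued at Week 24 but counted over 72 weeks has 24/72, a third, of the proper rate. That is one person, not an arm. Diabetes is excluded at entry, and Protocol 6.5 allows glucose-lowering drugs only once it develops. Applying the SAP 4.5 offset in SAP 4.5.5.4 is itself an inference, since that section names none.

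The rate models are conditional, and most safety output is counts and percentages. All of this limits size and scope. It does not remove the mismatch: on either reading the offset misses at least the 4-week follow-up, and nothing ends hypoglycemia time at risk at rescue.

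**Conclusion.** The point stands in a limited form. As written, SAP 4.5 pairs events to the end of participation with an offset covering a shorter, undefined period.

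- **Planned-period reading:** inflation of about 6%, nearly equal across arms, with little effect on rate ratios.
- **On-drug reading:** inflation depends on who stops, when, how long they are then followed, and whether events continue off drug. The range runs from none to about 1.35 in the cases worked above. Neither size nor direction of any bias between arms can be fixed from the documents.
- **Hypoglycemia:** if person-time runs past rescue, the episodes per patient per year are understated in an arm with more rescue, by about 3 to 6% in the ratio under the assumed 10% versus 1%. This acts against the inflation from off-drug events, and the net effect is unknown.

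Hypoglycemia incidence, the adverse event percentage tables and the efficacy endpoints do not use this offset and are unaffected. The required output at issue is the hypoglycemia rate; the model-based rates are affected only if they are run.

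**What to change.** In SAP 4.5, replace the undefined term with a stated time window for each rate analysis, and use that window for both the event count and the offset:

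- for rates on the Safety Analysis Set, first dose to end of study participation;
- for an on-drug rate, such as injection-site reactions, first dose to last dose plus 7 days, with events cut at the same date.

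In SAP 4.5.5.4, end both event counting and person-time at the start of rescue antihyperglycemic medication. Use that person-time for episodes per patient per year and for any rate model.

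The cost is a few sentences of SAP text and one derived variable, with no new data. It should be settled before database lock so that the denominator is not left to a programming choice.
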